***Class 1:**

- Urticaria (a type of rash)

- Hives

Class 2:

- Fever

- Chills

- Nausea

Class 3:

- Low Hematocrit (which refers to the percentage of whole blood that is made up of red blood cells) without evidence of bleeding

- High bilirubin fever (meaning there is a higher level of waste that hasn't been filtered out as it usually is when red blood cells breakdown).

Class 4:

- Oliguria (a reduction in the amount of urine being passed)

- Bleeding

- Hemoglobinemia (an excess of hemoglobin in the blood plasma)

- Hemoglobinuria (hemoglobin—the oxygen-transporting protein in blood—is at abnormally high levels)

- Transfusion associated circulatory overload

- shock

NOTE: * Class 1 reactions are to be expected and considered within normal range for this study

The subject will be observed during each transfusion for signs and symptoms of acute hemolytic reaction (i.e., chills, fever, low back pain, flushing, tachycardia, tachypnea, hypotension, red urine, shock, cardiac arrest). The subject will also be monitored

during the transfusion to minimize risk for potential infiltration or fluid overload due to rapid infusion of red blood cells (RBCs) or blood components.

Subjects with severe anemia and congestive heart failure are sensitive to circulatory overload.

The subject may also experience delayed transfusion reactions several hours to several days (delayed hemolytic reaction) after the transfusion is completed. Such reactions can include a febrile or pulmonary reaction (up to 6 hours) that may be associated with the blood administration.

Risks may include but not limited to transfusion reactions, bruising and/or soreness of arm in involved area, fatigue, boredom, and restlessness. To reduce the potential of any risks, subjects will be routinely asked for feedback on their current state. Some risks, such as arm bruising and soreness will be minimized by administration of procedure conducted only by qualified individuals. In the event of special precautions to be taken, such as the case of use of vulnerable populations (cognitively impaired adults), cognitive assessments before each session will be conducted to ensure the subjects ability to communicate any discomforts throughout the study.

- All adverse reactions reported after the start of the transfusions will be documented during trial.
- Transfusion reaction is an adverse event of a special interest, and any subject who experiences a transfusion reaction, in the opinion of the Transfusion Service or [name] and [name], will not be allowed to receive any further infusion.
 - In the event of discontinuation of infusions due to a transfusion reaction or other serious adverse event, a safety and efficacy follow-up assessments will take place 1 week after the last transfusion.

11. Cost to the Subject:

There will be no cost for the subjects; the subject will not be expected to pay for research participation.

12. Data Analysis & Statistical Considerations:

Endpoints include

- Primary Outcome Measure:

- Number of subjects with adverse events as a measure of safety and tolerability, and number of subjects who comply with the research protocol as a measure of feasibility.
- Secondary Outcome Measures:
 - Change on the UPDRS III/ IV off medication
 - Change in gait speed
 - Change in quantitative kinematics, FOG-Q
 - Change on the Parkinson's Disease Quality of Life Scale (PDQ-39)
 - Change on the Beck Anxiety Inventory (BAI)
 - Change on the Beck Depression Inventory (BDI)
 - Change in Trail Making Test A& B, Digit Symbol Test, Animal Naming Test, Phonemic Fluency (FAS), Matrix Reasoning, Block Design and Cogstate Maze Learning Test (Cog State)
 - Change in plasma biomarkers

13. Data & Safety Monitoring

Safety concerns regarding subject data include loss of subject data and disclosure of identification of participants. All electronically connected data will be securely stored in Stanford Medicine Box with Protected Health Information (PHI) & Personally Identifiable Information (PII) protection. Persons with access to this information include the Primary Investigator, research coordinator, and research team collecting data. Frequency of data monitoring will be as needed for data processing.

To ensure the subject's data and physical safety, continuous safety monitoring will occur throughout the study by the Safety Review Committee. The Safety Review Committee will include an on-call Neurologists, [name], [name], Psychologist [name], [name] and [name].

For any AEs outside of Stanford facility, the subject must call the research assistant at [name]. The research assistant will report AE to primary investigator and [name]. The subject will be told to seek medical assistance in nearest Emergency Department by them.

Research assistant will then need to file a SafeReport of the incident & document occurrence.

14. Privacy, Data Storage & Confidentiality

Subject confidentiality will be protected by electronically storing information using PHI and PII in Stanford Medicine Box. Persons with access to this information include the Primary Investigator, research coordinator, and research team collecting

data. Frequency of data monitoring will be as needed for data processing.

Table 1

Visit	Screening		Baseline	Transfusions to start within 2 weeks after the baseline- 2 transfusions per week								Outcome visits Same week of last transfusion		Post Eval 1 month after last transfusion	
	1 ON MEDS	2 OFF MEDS*	3	4 Week 1	5	6 Week 2	7	8 Week 3	9	10 Week 4	11	12 ON MEDS day after last transfusio n	13 OFF MEDS* day after visit 12	14 ON MEDS Four weeks after Visit 12	15 OFF MEDS* Day after visit 13
Informed consent	X														
Medication review	X														
Health History	X														
Physical Exam	X														
Neurological exam	X														
UPDRS III	X	X										X	X	X	X
UPDRS IV	X											X		X	
EKG		X													
MOCA	X														
SIP	X	X										X	X	X	X
SIP-Q	X	X										X	X	X	X
FOG-Q		X											X		X
rWFE	X	X										X	X	X	X
QGD	X	X										X	X	X	X
GaitRite/ FW	X	X										X	X	X	X

Trails A and B			X									X		X	
Digit Symbol Test			X									X		X	
Animal Naming Test			X									X		X	
Phonemic Fluency (FAS)			X									X		X	
WASI-II Block Design			X									X		X	
CogState- Maze Learning			X									X		X	
Matrix Reasoning			X									X		X	
Beck Anxiety Inventory			X									X		X	
Beck Depression Inventory			X									X		X	
PDQ-39			X									X		X	
Blood draw (research collect)			X									X		X	
Blood Labs			X									X		X	
Concomitant Med Review			X	X		X		X		X					
Adverse Events/ Tolerability				X	X	X	X	X	X	X	X				
Flow Sheet				X	X	X	X	X	X	X	X				
Transfusion				X	X	X	X	X	X	X	X

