 - Neuropsychiatric assessments: Beck Anxiety Inventory (BAI), Beck Depression Inventory (BDI), Parkinson's Disease Quality of Life Scale (PDQ-39)
 - Blood draw: 12 mL blood for central banking (these samples will be de-identified prior to further analysis and will be coded with a sample number, time of day and date of blood draw.
 - Blood Labs: metabolic and hematologic panels, Prothrombin Time (PT), Partial Prothrombin Time (PTT), Human Immunodeficiency Virus screen, Hepatitis B screen, Hepatitis C screen, IL6, uric acid, Apolipoprotein-

A1, direct bilirubin, homocysteine, ferritin, TNF, HIV Ag/Ab screen, ABO/Rh Typing and verification prior to first test agent administration

- **Plasma Transfusions (*starting within 2 weeks* of Baseline Assessment)**
 - Administer test agent twice weekly for 4 weeks (see transfusion protocol below)
 - Concomitant medication review
 - Adverse event/tolerability review, Flow Sheet-recording of vitals
 - Adverse events review per transfusion center protocol

- **Interim Assessment (on the week of last transfusion)**
 - Motor/Physical (ON and OFF medication)- UPDRS III/ IV, SIP, rWFE, QDG, GaitRite/FW, SIP-Q, FOG-Q
Neurocognitive assessments: Trail Making Test A& B, Digit Symbol Test, Animal Naming Test, Phonemic Fluency (FAS), Matrix Reasoning, Block Design, CogState Maze Learning Test (Cog State), ON medication
 - Neuropsychiatric assessments: Beck Anxiety Inventory (BAI), Beck Depression Inventory (BDI), PDQ-39, ON medication
 - Blood Draw (Lab collect)
 - Blood draw: Metabolic and Hematologic Panels, inflammation set

- **Final Assessment (*4 weeks after last transfusion*)**
 - Motor/Physical (ON and OFF medication)- UPDRS III/ IV, SIP, rWFE, QDG, GaitRite/FW, SIP-Q, FOG-Q
 - Neuropsychiatric assessments (BDI, BAI, PDQ-39), ON medication
 - Neurocognitive assessments Trail Making Test A& B, Digit Symbol Test, Animal Naming Test, Phonemic Fluency (FAS), Matrix Reasoning, Block Design, CogState Maze Learning Test (Cog State), ON medication
 - Blood Labs: Metabolic and Hematologic Panels, inflammation set,
 - Blood Draw: 12 mL blood for central banking

- **Transfusion Protocol**
 - Perform the transfusion according to the most current “Blood and Blood Component Administration” guidelines at Stanford Hospital & Clinic; in brief:
 - Check and record pre-transfusion baseline vital signs (temperature and blood pressure) within 1 hour prior to transfusion.
 - Obtain IV access

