Upon the inability to provide consent, diminished capacity will be assessed by a series of cognitive assessments to provide a clear position on whether subject has enough cognitive capacity to participate in this study. Cognitive assessments will be administered prior to starting the study.

9. Study Interventions:

Implanted devices included but not limited to birth control methods, heart pacers, brain stimulators, etc. may intervene with the study. Subject will be asked if they have any implanted devices during prescreening.

10. Risk/Benefit Assessment:

Blood products carry risks of virus, hepatitis and HIV infection. Acute transfusion reactions could include such signs and symptoms as the following, divided into classes to denote the level of severity.

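### No blood count is scheduled while infusions can still be withheld, so a symptom-free fall in hematocrit, a listed Class 3 reaction, would first show after the eighth unit

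*Combined protocol and SAP*

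**What the plan says.** Section 10 (Risk/Benefit Assessment) introduces a list of possible reactions: "Acute transfusion reactions could include such signs and symptoms as the following, divided into classes to denote the level of severity". Class 3, the second highest of four, contains "Low Hematocrit (which refers to the percentage of whole blood that is made up of red blood cells) without evidence of bleeding" and an item headed "High bilirubin fever". A later paragraph of the section adds: "The subject may also experience delayed transfusion reactions several hours to several days (delayed hemolytic reaction) after the transfusion is completed".

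The section closes with a stopping rule. It makes transfusion reaction an adverse event of special interest and says that "any subject who experiences a transfusion reaction, in the opinion of the Transfusion Service" or of the named study physicians, "will not be allowed to receive any further infusion". Section 13 states that "continuous safety monitoring will occur throughout the study by the Safety Review Committee".

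Section 5 lists hematologic panels at the Baseline, Interim and Final Assessments. Table 1 marks Blood Labs at Visits 3, 12 and 14, and transfusions at Visits 4 to 11, two per week. It sets Visit 12 on the day after the last transfusion. At the transfusion visits the table shows adverse event review and the flow sheet every time, and concomitant medication review at some visits. It shows no laboratory test there.

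**The concern.** Hematocrit is a laboratory value. Vital signs, observation and questions about symptoms do not measure it. A fall that causes no symptoms can become known only through a blood test, and the first one scheduled after baseline comes when no unit is left to withhold.

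Two things are at stake. The physicians who judge whether a reaction has occurred, and the Safety Review Committee, have no scheduled blood result during the eight infusions. And a low value at Visit 12, with no mid-course value beside it, could not be tied to a unit and would be hard to tell apart from dilution by the plasma already given. This matters because safety and tolerability are the primary objective (Section 5).

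**Working it through.** The plan gives no figure of its own on this point, so the check is a count from Table 1.

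**Schedule.** Units 1 to 8 are given at Visits 4 to 11, so unit *k* is at Visit *k* + 3. Blood labs are at Visits 3, 12 and 14. Panels at the transfusion visits: 0 of 8. After unit 1 there are 7 decisions to give a further unit, and none has a scheduled hematocrit behind it.

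**Further units before a result is available.** Assume that a fall starts after unit *k*, is present at the next draw and lasts. A draw before unit *d* is read before unit *d* + 1. If *d* is the next draw after the fall starts (*k* < *d*), then *d* − *k* further units are given before the result can be read. If no mid-course draw remains, the number is 8 − *k*. Means weight the eight starting points equally, which is also an assumption.

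| Fall starts after unit | 1 | 2 | 3 | 4 | 5 | 6 | 7 | 8 | Sum | Mean | Worst |
|---|---|---|---|---|---|---|---|---|---|---|---|
| Current plan | 7 | 6 | 5 | 4 | 3 | 2 | 1 | 0 | 28 | 28/8 = 3.5 | 7 |
| One panel, Visit 7 (*d* = 4) | 3 | 2 | 1 | 4 | 3 | 2 | 1 | 0 | 16 | 16/8 = 2.0 | 4 |
| Panels at Visits 5, 7, 9 (*d* = 2, 4, 6) | 1 | 2 | 1 | 2 | 1 | 2 | 1 | 0 | 10 | 10/8 = 1.25 | 2 |

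With the single Visit 7 panel, the reduction is 4 units for each of the first three starting points (3 × 4 = 12 = 28 − 16) and zero for the other five.

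**Dilution.** Suppose, as an upper bound, that all infused plasma stays in the circulation. Take units of 200 to 300 ml, a blood volume of 4 to 6 L and a starting hematocrit of 42; none of these is in the documents. After *n* units of *u* litres in blood volume *V*, the fall in points is 42 × (1 − *V*/(*V* + *u n*)). The low end uses *V* = 6, *u* = 0.2; the high end uses *V* = 4, *u* = 0.3.

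| Draw | Units already given | Fall from dilution alone (points) |
|---|---|---|
| Visit 5 | 1 | 1.4 to 2.9 |
| Visit 7 | 3 | 3.8 to 7.7 |
| Visit 9 | 5 | 6.0 to 11.5 |
| Visit 12 | 8 | 8.8 to 15.8 |

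Actual falls should be smaller as the body clears the volume. On this bound, dilution at Visit 7 is about half that at Visit 12 or less, but not negligible.

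**The case against.** The strongest reply is that the plan breaks no rule of its own. That stands. A reader might infer that low hematocrit is an automatic stop that the schedule makes unworkable. The documents do not say so: the class list describes what a reaction could include, and stopping rests on medical opinion. Nor does the sentence on continuous monitoring in Section 13 promise any laboratory schedule.

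Existing coverage is also substantial. Section 5 provides for vital signs, a supervised stay, and instructions on delayed reactions; Section 10 adds observation for signs of acute hemolysis; Table 1 has adverse event review at all eight infusions. Suspected reactions follow hospital guidelines, and adverse event review follows a transfusion center protocol. Neither text is shown, and either may add tests. Testing prompted by suspicion would not catch a fall that raises none, but routine testing under those procedures cannot be ruled out.

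A reader might also infer that the primary outcome, the number of subjects with adverse events (Section 12), is compromised. For a lasting fall it is not: the Visit 12 panel would record it, and a count of subjects does not need the date.

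Three further limits stand. The documents give no rate for symptom-free falls. A single Visit 7 draw does nothing for falls starting after unit 4 or later. And that draw is itself affected by dilution.

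One reply carries little weight. Section 5 places the Interim Assessment only in the week of the last transfusion, which might allow an earlier draw. Table 1 fixes Visit 12 to the day after that transfusion, and the looser reading would bear on the eighth unit at most.

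**Conclusion.** The point holds as a cheap improvement, not as an inconsistency in the plan. No scheduled result can show a symptom-free fall in hematocrit before the eighth unit has been given. The loss is the opportunity to withhold later units and to place the fall in time.

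The sizes rest on a fall that lasts and on equal weight for each starting point. They count units given before a result is available. It would be tempting to read them as units avoided, but the decision to stop stays with the physicians, so a readable result does not guarantee a stop. With the frequency of such falls unknown and reactions with symptoms already covered, the priority is modest and confidence is medium.

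**What to change.** Add one hematologic panel with bilirubin to Table 1 and Section 5, drawn before the unit at Visit 7 and read before the unit at Visit 8. Visit 7 is the second infusion of week 2 and Visit 8 opens week 3, so nobody waits for a same-day result. The Transfusion Service or the study physicians would judge the result under the existing rule in Section 10, using bilirubin and allowing for plasma already given. No fixed numeric stop is needed. Draws at Visits 5 and 9 as well are optional.

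Cost: 15 subjects × 1 draw = 15 panels, or 15 × 3 = 45 with the optional draws. The total would be slightly higher if dosed subjects drop out and are replaced, because 15 is the number meant to complete. Add review time and an occasional work-up for a fall that proves to be dilution. The draws fit existing visits at which IV access is obtained anyway, so no visit is added.

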- Subject's positive test results for Hepatitis B, Hepatitis C or HIV at screening
- Any other condition or situation that the investigator believes may interfere with the safety of the subject or the intent and conduct of the study
- Subject's medical history of:
 - Stroke

- Anaphylaxis
- Gout- may cause an increase in uric acid
- Prior adverse reaction to any human blood product
- Any history of a blood coagulation disorder or hypercoagulability
- Congestive heart failure
- Uncontrolled hypertension
- Renal failure
- Prior intolerance to intravenous fluids
- Recent history of uncontrolled atrial fibrillation
- IgA deficiency (by history)
- Subject's relation to medications or other treatments:
 - Any concurrent use of an anticoagulant therapy. Antiplatelet drugs (e.g., aspirin or clopidogrel) are acceptable.
 - The use of Inosine, which may alter urate levels
 - Concurrent participation in another interventional treatment trial for Parkinson's disease. If there was prior participation, the last dose of the investigational agent must have been at least 6 months prior to Screening.
 - Treatment with any human blood product, including intravenous immunoglobulin, during the 6 months prior to Screening or during the trial.
 - Concurrent daily treatment with benzodiazepines, typical or atypical antipsychotics, long-acting opioids, or other medications that, in the investigator's opinion, interfere with cognition. Intermittent treatment with short-acting benzodiazepines or atypical antipsychotics may be permitted, provided that no dose is administered within the 72 hours preceding any cognitive assessment.

Ineligible Subjects

Ineligible subjects will be notified of their ineligibility. Ineligible subjects will be asked if their information could be kept on files in the event of being qualified to participate in future studies. If subjects do not want their information on file, all data collected will be destroyed. Only participating subjects will be used for analysis.

5. Design & Procedures

We will evaluate a dose of one Plasma unit transfusion twice per week (obtained from male subjects between the ages of 18-25) for four weeks in 15 study subjects with PD. The study will be open-label and an end point at eight weeks after the first week of transfusions.

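### The primary outcome counts subjects with adverse events, but no adverse-event review is scheduled after the eighth infusion (Visits 12–15), so late first events may be missed.

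*Combined protocol and SAP*

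**What the plan says.** Section 12 defines the safety part of the primary outcome as "Number of subjects with adverse events as a measure of safety and tolerability". It gives no start or end date for the count.

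Adverse-event collection is scheduled in two places, and they agree:

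- Table 1 marks "Adverse Events/ Tolerability" at Visits 4 to 11, the same columns as the infusions. Visits 12–15 are blank in that row.
- Section 5, under Plasma Transfusions, lists "Adverse event/tolerability review, Flow Sheet-recording of vitals" and "Adverse events review per transfusion center protocol". Neither item appears under the Interim or Final Assessment, although both lists itemise motor, cognitive, mood and blood measures.

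Follow-up runs well past the last infusion. Section 5 says: "The study will be open-label and an end point at eight weeks after the first week of transfusions". It places the Final Assessment "4 weeks after last transfusion". Post-baseline laboratory work falls only at Visits 12 and 14; the Interim list, for example, has "Blood draw: Metabolic and Hematologic Panels, inflammation set".

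Section 10 warns that reactions can appear hours to days after an infusion, lists low hematocrit and raised bilirubin among the signs, and makes a transfusion reaction an event of special interest.

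Section 5 lists "Concomitant medication review" under Plasma Transfusions without limiting it to particular visits. Table 1 marks it at Visits 3, 4, 6, 8 and 10 only.

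**The concern.** A count of subjects with events depends on how events are sought. Up to Visit 11, subjects are asked at every infusion visit. From Visit 12 on, the schedule contains no such question, so the count changes from solicited to mainly volunteered reporting partway through follow-up. A subject whose first event begins after the eighth infusion, or shows only in the Visit 12 or 14 blood results, may be recorded as event-free. The error can only make the treatment look safer, in a study whose stated purpose is to show safety.

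The gap also falls at an awkward point. After each of infusions 1–7, the next infusion visit is an occasion to ask about delayed effects. After the eighth there is none.

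A lesser, separate point affects the secondary outcomes. A medication change in the four weeks or so before Visit 14 could go unrecorded and be read as a change in motor, mood or cognitive scores.

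**Working it through.** The plan gives no event rate, power or precision figure for this outcome, so there is none to reproduce. The check is of the schedule and its intervals.

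**Marks in Table 1, by visit**

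| Row | Visits marked |
|---|---|
| Transfusion | 4–11 |
| Adverse events | 4–11 |
| Medication review | 3, 4, 6, 8, 10 |
| Blood labs | 3, 12, 14 |
| UPDRS III | 1, 2, 12–15 |

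Other rows do carry marks at Visits 12–15, so the blanks in the adverse-event row are not lost columns.

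**Timing inputs**

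- Visit 11 is the eighth infusion. Visit 12 is one day later, Visit 13 a day after that, and Visit 14 four weeks after Visit 12 (Table 1).
- Section 5 instead counts four weeks from the last infusion to the Final Assessment.
- The spacing *s* between the two infusions in a week is not stated. I assume *s* = 2 to 4 days and weekly cycles.

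**Time without a scheduled review**

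- Visit 11 to Visit 14: 1 + 28 = 29 days (Table 1), or 28 days (Section 5).
- Visit 13 to Visit 14, with no visit between: 29 − 2 = 27 days, or 28 − 2 = 26 days.

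**Share of follow-up**

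- First to eighth infusion: 21 + *s* = 23 to 25 days.
- First infusion to Visit 14: 52–54 days (Table 1), or 51–53 days (Section 5).
- Share after the last review: 29/52 = 55.8% and 29/54 = 53.7%; 28/51 = 54.9% and 28/53 = 52.8%. The range is 53%–56%.
- Taking the Section 5 end point literally, 7 + 56 = 63 days, the share is (63 − 25)/63 = 60% to (63 − 23)/63 = 63%.

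**Effect on the count**

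- Each missed subject among 15 is 1/15 = 6.7 percentage points.
- Let *q* be a subject's chance of a first event in the uncovered period (assumed). The expected number of such subjects is 15*q*, and the chance of at least one is 1 − (1 − *q*)^15.

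| *q* | Expected subjects | Chance of at least one |
|---|---|---|
| 2% | 0.3 | 26.1% |
| 5% | 0.75 | 53.7% |
| 10% | 1.5 | 79.4% |
| 20% | 3.0 | 96.5% |

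These are subjects exposed to being missed. The undercount itself would be smaller, because volunteered reports would catch some of them.

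**Medication review to Visit 14**

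- From Visit 10: *s* + 28 to *s* + 29, which is 30–33 days.
- From Visit 11, if Section 5 is read as covering every infusion visit: 28–29 days.

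**The case against.** The strongest reply is that late events are not ignored. Section 10 says subjects will regularly be asked how they are and that reported reactions are documented. Section 5 has them told whom to contact about a delayed reaction. Section 13 requires a call for events outside the facility, followed by a report to the investigator and a filed incident report, and has a committee monitoring safety throughout. Subjects attend in person on the two days after the eighth infusion, with bloods at Visit 12. A partner journal exists, though the partner is optional. The transfusion center's own procedures, which are not in the document, may cover delayed reactions. This stands as far as it goes: collection continues, and the defect is a lost prompt. But none of these steps is tied to a visit after Visit 11. The one dedicated safety follow-up, a week after the last infusion, applies only to subjects whose infusions are stopped for a reaction or other serious event.

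Second, 53%–56% is calendar time and not risk. That is right. Delayed reactions cluster in the days after an infusion, those after infusions 1–7 would largely be picked up at the next visit, and only subjects with no earlier event can change the count. The percentage should not be read as a share of events missed.

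Third, the dates are loose. Table 1 places Visit 15 a day after Visit 13, which does not fit its place after Visit 14 and is probably a slip. The literal eight-week end point lengthens the gap. The figure of 15 is a goal for completers, so the number infused may be larger and each subject's weight smaller. None of this removes the gap.

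Fourth, medication review is a different matter and Section 4 already requires stable dopaminergic dosing to study end. It is separate, but a requirement is not a check that it was met.

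**Conclusion.** The concern holds. As written, the primary adverse-event count has no scheduled review for the 28–29 days from the eighth infusion to Visit 14, although subjects attend during and at the end of that time. The last blood results that could show a reaction arrive after the final scheduled review, and no step carries them into the count. The interval follows directly from the document; the 53%–56% share also needs the assumed 2–4 day spacing. How many subjects would be missed cannot be derived, and the values of *q* above are illustrations. Confidence is high in the reading of the schedule, and does not extend to any particular undercount. This should be fixed, but it does not invalidate the design. The medication-review gap is real and secondary.

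**What to change.** - In Table 1, mark adverse-event review at Visits 12–15 and medication review at Visits 12 and 14. Add both to the Interim and Final Assessment lists in Section 5.
- In Section 12, state that the count runs from the first infusion through the Final Assessment and includes Visit 12 and 14 laboratory abnormalities that the investigator judges to be adverse events.
- Reconcile the frequency of medication review between Section 5 and Table 1, and correct the date given for Visit 15.

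No visit or subject is added. The cost is a few minutes at each of these visits and the edits themselves. The count may look less favourable, because it would be more complete.
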